# Research/trial program: **The Swedish Essential Tremor (SWEET) Trial** – A Multicentre Randomized Controlled Trial of Deep Brain Stimulation for Essential Tremor

# PURPOSE AND AIMS

- Aim 1 To evaluate the effect of deep brain stimulation (DBS) vs best medical treatment in essential tremor (ET) in a randomized, single-blinded controlled trial.
- Aim 2 To compare the effect of DBS in the established target in the ventrolateral (VL)thalamus/ nucleus ventralis intermedius thalami (Vim) and in a new target in the posterior subthalamic area (PSA)/caudal Zona incerta (cZi).
- Aim 3 To map the target area in the VL-thalamus and PSA concerning effects and side effects of stimulation in order to identify and delineate the optimal target.
- Aim 4 To evaluate the long-term effects of DBS for ET in a longitudinal nonrandomized evaluation.

**SURVEY OF THE FIELD Deep Brain Stimulation (DBS)** 

In DBS, thin quadripolar electrode leads (with four 1.5 mm long and 1.27 mm thick contacts, separated by 1.5 mm space), connected to a neuropacemaker are implanted with stereotactic technique into

the central parts of the brain (Figure 1) where the neuronal activity is modulated with electrical current. DBS has

revolutionised the treatment of Parkinson's disease and other

Figure 1. Implanted DBS system

movement disorders, and more than 150.000 patients have so far been operated. Currently, new indications and targets are emerging.

However, many of the brain targets subjected for DBS are not well defined, and one of the main problem with DBS is likely to be the high number of suboptimally placed electrodes with lack of effect, unacceptable side effects and costly revisions. Further, even though this is an invasive and highly resource demanding therapy, most clinical indications for DBS (asides from Parkinson's disease and dystonia) are not evidence based, . They are considered as "established treatments" and often provided as clinical treatment and not within the context of trials or scientific studies.

## **DBS for Essential Tremor**

ET is the most common adult movement disorder with a prevalence of about 5% in the population above 65 years of age. Of patients who seek medical care up to 50% do not respond adequately to drug therapy.

The thalamic nucleus ventralis intermedius (Vim) is the projection structure of the cerebello-thalamic fibres mediating tremor. Hence, Vim has been an "established" target for surgical treatment of ET during the thalamotomy era, and when DBS was introduced and replaced thalamotomy, the Vim was logically the target for DBS for tremor. However, data from recent years indicate that it might not be stimulation of the Vim itself, but rather, the stimulation was affecting the pathologic tremor oscillations mediated by the cerebellothalamic-cortical projections, located in the PSA and the caudal zona incerta (cZi). Thus, a number of studies have demonstrated that electrode contacts that reach the PSA have a better effect on tremor than those located more dorsally-rostrally in the Vim. This subthalamic area, which is situated immediately ventral-caudal to the Vim, is particulary dense with cerebello-thalamic axons, dispersing into the Vim. Stimulation is thus likely to involve more axons in the PSA than in the Vim, since these axons in the PSA constitute so to speak a bottle neck of the axonal traffic mediating tremor. It is also plausible that stimulation of axons rather than stimulation of nuclei actually affects by antedromic and orthodromic propagation more neurons and therefore also alters tremor oscillations more efficiently . A number of studies directly targeting the cZi have also recently presented results comparing favorably with the results published for Vim DBS.

#### Level of evidence regarding DBS in ET:

Neither the Vim nor the cZi are evidence based targets, and there are no evidence-based DBS procedures for ET (level IV evidence only), even though this is the second most common indication for DBS. However, the Vim is by tradition the established target for ET and the procedure is recommended in the Swedish guidelines for treatment of tremor.

The results of Vim DBS ET have been demonstrated in a number of uncontrolled, mostly minor studies. A problem is that many of these studies are likely to contain electrodes placed blindly within the PSA and that the actual location of the active electrode contacts of the DBS lead is seldom taken into consideration. Further, many reports lack a preoperative baseline and the results are often reported in a heterogenous manner, making comparison between different studies difficult. Regarding cZi DBS, excluding our own studies, the results of cZi DBS in 33 patients have been presented in five small and non-randomized studies. Concerning the relative merits of the two targets, we have previously presented a tremor reduction of 86 % following cZi, compared to only 60% in the Vim^4, and demonstrated that the electrode contacts with the best effect in what was called Vim were often placed in the PSA. There is further a scarcity of long-term data regarding both targets.

#### Identifying the brain target in the individual patient

[figure not shown]
In a recent study of 28 000 procedures, electrode revisions constituted up to one third of all DBS procedures. It is likely that misplaced electrodes due to difficulties in identifying the target is one of the major causes explaining a poor result in DBS for movement disorders.

There are a number of different ways in which the target can be identified. Even for brain targets that can be visually identified on MRI, some centres rely mostly on statistical coordinates of the targets based on anatomical atlases, but this may result in poorly placed electrodes, due to significant inter-individual differences in the anatomy. However, concerning the Vim, identification of that target in relation to ventricular landmarks is a necessity since the Vim cannot be visualized as such in MRI.

Currently, 60 % of the centres are relying on micro-electrode recording (MER) in order to identify the target in the individual patient. This is an invasive neurophysiological method necessitating considerable resources. It is also associated with an increased risk of haemorrhages, since it involves introducing several sharp cannulas and electrodes into the target area. The third method is visual anatomical targeting, whereby the target is identified on the patients' MRI, either directly or in relation to visible very closely related landmarks (Figure 2). We have over the years made significant contributions in the development of this last method, both concerning the pallidum^26, STN and cZi. Unfortunately this method demands a high level of dedication and relies to a high degree on personal experience.

Scientifically based guidelines delineating the target areas and identifying the optimal target do not readily exist.

Common for all different methods is that it is normally required that the patient is awake during surgery in order to allow for intra-operative testing of effect/side effects, even if some today perform the procedure in general anaesthesia concerning some of the targets. If the brain targets could be identified with a high degree of certainty, and the electrode position within that target can be verified during surgery, then having the patients awake during surgery would no longer be necessary.

**Figure 2)**. Example of visual anatomical targeting. In the enlarged MRI section (B) one electrode is place in the STN, and one electrode more posterior in the cZi. A schematic representation (C) demonstrate the relation of the electrodes to the STN and red nucleus.

#### Identifying and delineating the optimal targets

The literature regarding optimal target point/volume for the different targets is surprisingly meagre. The most common target, the subthalamic nucleus (STN), is also the most studied regarding this issue, but the effect has been evaluated in relation to the location of the electrode in no more than 260 patients in a total of 13 different studies. Interestingly, most of these studies have found that the best effect is not achieved in the target structure itself, but in another adjacent structure, the more rostral part of the Zona incerta overlying the STN. The same is true regarding the few studies of thalamic surgery for tremor, where most have demonstrated that the best effect is achieved from contacts outside the thalamic target, in the PSA. Concerning other targets/indications the literature is even more limited.

The existing studies are further hampered by the heterogeneity of the methods. Often it is not the actual location of the electrode that is reported, but the intended one. Even when the actual location is reported it is most often presented according to distant landmarks, even if the targeting was done visually, which is a significant problem, taking into consideration the inter-individual variability. Further, even though the stimulation parameters used can differ widely and hence the electrical current affect different neighbouring structures, this is virtually never taken into account.

## DBS for ET – Conclusions and aim

DBS for ET is thus not an evidence based therapy and the same is true regarding both target areas used for ET. The relative merits of the different targets used have not been clearly demonstrated and the individual targets are not well delineated. There is thus a need to address these issues.

## **PROJECT DESCRIPTION**

#### Overview - What are we going to study?

The effect of DBS for ET will be evaluated in a multicentre study recruiting 100 patients randomized to immediate surgery (group A) or best medical treatment only (as decided by the movement disorder neurologist, with few exceptions likely to be identical to their current medication) with delayed surgery at 6 months if still needed /indicated (group B). Primary outcome is tremor reduction as measured with Essential tremor rating scale (ETRS), with focus on items 5/6 (hand tremor) & 11-14 (hand function), at baseline before surgery and at 6 months. Secondary outcome includes quality of life measured with QUEST and electrical energy consumption. After 6 months group B is operated –as indicated-, and group A and B are thereafter evaluated as one single group for long-term effects and analyses of electrode location. The electrodes will in all patients be inserted with a trajectory developed for this study allowing stimulation both in the established and traditionally used target Vim as well as in the new target cZi. Each contact will be evaluated individually concerning location, effects and side effects, in relation to stimulation parameters. This is done in order to, a) compare the two targets, but more importantly, b) to create a map of the whole area with identification/delineation of the optimal target point/volume. The time necessary to gather

100 patients is estimated to 2.5 - 3 years.

#### Study design:

- Step 1 is designed as a randomized controlled trial in order to compare the effect of DBS (Group A) and medical treatment (Group B) on ET (Aim 1).
- In step 2 4 the patients in group A are operated and group A and B joined into one single group.
  - Step 2 all electrode contacts are individually analysed regarding chronic and acute stimulation effects in relation to their location in either the Vim or the cZi in order to decide which target is more effective (Aim 2).
  - Step 3 Effects and side effects, with consideration to field of stimulation, are analyzed in relation to neighboring structures in order to map the whole area and delineate the optimal target points (Aim 3).
  - Step 4 The long-term effect is evaluated in a non-randomized longitudinal study at 1, 3, 5, 10 years (Aim 4).

#### 0

## Sample size and power:

In step 1, with a confidence interval of 95%, and an expected improvement of 85 % in the surgical group and none (or at least < 25%) in the medical group, regarding contralateral items 5/6 & 11-14, a power of 100 % is achieved. In step 2, with an expected improvement of 85% in one target and 60% in the other, a power of 98% is achieved. The high number of patients is, however, necessary for step 3, mapping of the area, in order to give a good cover of the periphery (Length of contact carrying electrode surface 7.5 mm, expected mean non-random intended deviation from target point (as defined in the study) 1 mm, expected mean random deviation from intended target point 1.5 mm). Based on the previous experience, less than 5% of patients is expected to be lost during the follow up, which will have an insignificant effect on the power.

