#### Surgery

[figure not shown]
The patients are implanted using a trajectory targeting both the traditional target in the Vim and the new target in the cZi, with electrode contacts in both structures. Variations in the anatomy of the individual patient in combination with random deviations from the intended target point, will guarantee a spread of electrode contacts through the area of interest (Figure 3).

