## **Evaluation of stimulation**

Tremor is measured with  $ETRS^{11}$  (with focus on items 5/6 (hand tremor) & 11-14 (hand function). ETRS is performed before surgery at baseline and at 6 months on/off med/stim. The evaluation is done blinded to the patients in the surgical group. The evaluation is documented on video (with the patient wearing a head cap) and

segmented for blinded evaluation of two expert evaluators. In the second step all individual electrode contacts are evaluated in the same manner regarding tremor, but also regarding side effects, with standardized stimulation parameters and a gradual increase of voltage (Figure 4).

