#### **Statistics:**

Two-tailed T-test will be used for continuous variables, Wilcoxon signed rank test for paired non-parametric data and Mann-Whitney U test for un-paired non-parametric data. The model of stimulation fields, Volumes of Neural Activation (VNAs), will be generated using simulations of homogeneous tissue with density compensated probabilistic stimulation

maps. Registercentrum Norr will be responsible for the statistical analyses and stimulation field analysis will be done by Medtronic Eindhoven Design Center for Neuromodulation.

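### Is the 98% power for comparing the two targets unusable because no SD, test or number per target is given?

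*Protocol*

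**What the plan says.** The protocol's section on sample size and power gives one sentence to step 2: "In step 2, with an expected improvement of 85% in one target and 60% in the other, a power of 98% is achieved". The 95% level appears only in the preceding sentence, on step 1. The same section attributes the large patient number to step 3, the mapping of the area, and allows for attrition with "less than 5% of patients is expected to be lost during the follow up".

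The percentages match the background section on the level of evidence, where "we have previously presented a tremor reduction of 86 % following cZi, compared to only 60% in the Vim". They are reductions in a tremor score, not shares of patients who respond.

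On the analysis, the Statistics section lists a two-tailed t-test for continuous variables, then "Wilcoxon signed rank test for paired non-parametric data and Mann-Whitney U test for un-paired non-parametric data". It assigns none of these to step 2 and lists no test of proportions. Under Study design, "all electrode contacts are individually analysed regarding chronic and acute stimulation effects in relation to their location in either the Vim or the cZi"; under Evaluation of stimulation, "In the second step all individual electrode contacts are evaluated in the same manner regarding tremor". The Surgery section describes a trajectory "targeting both the traditional target in the Vim and the new target in the cZi, with electrode contacts in both structures". The Overview sets 100 randomised patients and gives the control group "delayed surgery at 6 months if still needed /indicated (group B").

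**The concern.** A difference between two mean improvements fixes a power only together with an SD, a test and a number of observations, and the sample size section gives none of these for step 2. Several readings are open. The data could be treated as paired, since each lead should have contacts in both targets, or as unpaired. The count could be of patients or of contacts. The number of patients is itself uncertain, because group B is operated on only where surgery is still indicated, while the only stated reduction is a small loss to follow-up.

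There is also a more specific suspicion. If 85% and 60% were entered as responder proportions, the calculation does not match the outcome, a rating-scale score. The power for Aim 2 would then rest on the wrong formula, and a reader could not see how it moves if fewer patients are operated on.

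**Working it through.** **Inputs.** From the protocol: improvements of 85% and 60% (difference 25 points), 100 patients, 95% level. Assumed: the 95% level carries over to step 2 as two-sided 0.05. No SD is given, so every SD below is an assumption.

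**1. Reproducing 98% from the printed figures.** Treat 0.85 and 0.60 as independent proportions with n = 100 per target and pooled proportion 0.725:

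- Term under the null: 1.96 × √(2 × 0.725 × 0.275 / 100) = 1.96 × 0.0631 = 0.1238
- SE under the alternative: √((0.85 × 0.15 + 0.60 × 0.40) / 100) = √(0.3675 / 100) = 0.0606
- z = (0.25 − 0.1238) / 0.0606 = 2.08, so power = 98.1%

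Variants agree closely: unpooled 98.5%, arcsine 98.2%, continuity-corrected 97.2%, Fisher exact 97.4%. The step 1 figure fits the same reading: 85% against 25% with an assumed 50 per arm gives more than 99.9%, printed as 100%. The match suggests that a two-proportion formula was used; it does not prove it.

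**2. A comparison of means.** For a difference of 25 points, the SD that gives 98% power (t-test, two-sided 0.05) is:

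| Comparison | Number | SD for 98% power |
|---|---|---|
| Unpaired | 100 per target | 43.8 |
| Unpaired | 50 per target | 30.8 |
| Paired (SD of difference) | 100 pairs | 61.7 |
| Paired (SD of difference) | 95 pairs | 60.1 |

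A smaller SD gives more than 98% and a larger one gives less.

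**3. How large could the paired SD be?** Assume that percent improvement lies between 0 and 100 (worsening would widen this). A mean of 85 then caps the SD at √(85 × 15) = 35.7, and a mean of 60 at √(60 × 40) = 49.0. If the two are uncorrelated, the SD of the difference is at most √(35.7² + 49.0²) = 60.6. That is the same variance, 0.3675, as in step 1, so the two-proportion formula nearly equals the paired calculation at this cap. A graded score, or a positive correlation within patients, lowers the SD. With 100 pairs, power at SD 50 is 99.9%.

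**4. Fewer patients in step 2.** The protocol gives no expected share of group B operated on. The rows below 95 are illustrations only, assuming 50 patients in each randomised group.

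| Number per target | Two proportions | Paired, SD 50 | Paired, SD 60 |
|---|---|---|---|
| 100 | 98.1% | 99.9% | 98.5% |
| 95 (5% lost) | 97.6% | 99.8% | 98.0% |
| 75 (half of group B) | 93.7% | 99.0% | 94.5% |
| 71 (75 less 5%) | 92.4% | 98.6% | 93.4% |
| 50 (no group B surgery) | 80.9% | 93.4% | 82.3% |

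At SD 61.7, 71 pairs give 92.0%. No fixed floor can be claimed, since the result depends on the SD and share chosen.

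**5. How likely are the lower rows?** The section on ethical considerations says that patients are approached only once they have been accepted for DBS. The Population section requires more than five years of symptoms, substantial incapacity, and poor effect or poor tolerance of drugs. The Overview expects medication in group B to stay largely as it was. Surgery in nearly all of group B is the natural reading, and that keeps the count near the upper rows.

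**The case for a change.** The strongest case for a change is that the protocol prints the figure itself, so the inputs belong beside it, and a later analysis plan cannot repair a number already stated here. Matching a formula that does not fit the outcome, the listed tests or the within-patient layout does not verify the planned comparison. On the two-proportion reading, power is sensitive to how many group B patients are operated on, and the protocol does not show this. Adding the inputs would take only a sentence or two.

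Much of this stands as description. The method is not stated, and the figure cannot be confirmed for a comparison of scores. What does not stand is the step to a needed change. The choice of test and whether patients or contacts are the unit are commonly left to the analysis plan, which is not at hand. A recalculation from means would need an SD that the protocol does not give and could move the power either way; on the bounded-score argument above, upward is at least as plausible. The low powers need shares of group B surgery that nothing in the text supports.

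**Conclusion.** No change follows. The SD, test and number per target are missing for step 2, but 98% is recovered from the protocol's own 85%, 60% and 100 patients (98.1%, two proportions, two-sided 0.05), and a paired comparison of 100 patients reaches the same value at an SD of the difference near 62 points. Entering mean improvements as proportions is a plausible but unproven explanation; if it happened, it is close to assuming the widest spread that a 0 to 100 score allows for uncorrelated responses, so it need not flatter the power. The 5% loss foreseen in the protocol takes the two-proportion figure only to 97.6%. The patient number rests on the mapping step, and the Overview ranks that map above the target comparison. This is missing reporting detail whose completion would leave the number of patients, the design, the analysis and the conclusions as they are. The judgement assumes that most of group B goes on to surgery, as enrolment after acceptance for DBS implies, and that the analysts compare the targets with a test suited to contacts lying within the same patients.

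### Does the 7.5 mm contact length behind the mapping rationale conflict with the 10.5 mm lead described in the background?

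*Protocol*

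**What the plan says.** Two places in the protocol bear on lead geometry.

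- The background section *Survey of the field: Deep Brain Stimulation (DBS)* describes the therapy in general. It begins "In DBS, thin quadripolar electrode leads" and gives the layout as "with four 1.5 mm long and 1.27 mm thick contacts, separated by 1.5 mm space".
- *Sample size and power* first reports the powers for the two efficacy steps: for Step 1 "a power of 100 % is achieved", and for Step 2 a power of 98%. It then says: "The high number of patients is, however, necessary for step 3, mapping of the area, in order to give a good cover of the periphery". Three figures follow in parentheses: "Length of contact carrying electrode surface 7.5 mm", "expected mean non-random intended deviation from target point (as defined in the study) 1 mm" and "expected mean random deviation from intended target point 1.5 mm".

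The planned number of patients is 100 (*Overview*). *Target analysis* has two experts determine where each contact actually lies from fused preoperative and postoperative imaging, and has the stimulation parameters recorded so that the stimulated field can be mapped.

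**The concern.** The only lead layout written out in the protocol does not give the length used in the sample-size section. That section presents mapping coverage as the reason for the large sample and supports it with three numbers, of which the contact-carrying length is the only one describing extent along the lead. If it were wrong, the coverage argument for 100 patients would seem to rest on a lead other than the one described.

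Geometry also matters to Aims 2 and 3. A single trajectory is meant to place contacts in both Vim and cZi, and each contact is evaluated individually. A longer lead with wider gaps reaches further along the track but samples it more thinly. It might also put a different number of contacts in each structure.

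**Working it through.** **Inputs.** From the background survey: 4 contacts, each 1.5 mm long, with 1.5 mm gaps (3 gaps). From *Sample size and power*: contact-carrying length 7.5 mm, intended deviation 1 mm, random deviation 1.5 mm, powers 100% and 98%. From *Overview*: 100 patients.

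**Step 1: try to reproduce 7.5 mm from the described lead.**

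| Reading | Formula | Result |
|---|---|---|
| Edge to edge | 4 x 1.5 + 3 x 1.5 | 10.5 mm |
| Centre to centre | 3 x (1.5 + 1.5) | 9.0 mm |
| Contact metal only | 4 x 1.5 | 6.0 mm |
| Half a gap added at each end | 4 x (1.5 + 1.5) | 12.0 mm |

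None gives 7.5 mm. The edge-to-edge ratio is 10.5 / 7.5 = 1.40.

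**Step 2: ask what would give 7.5 mm.** Four 1.5 mm contacts span 7.5 mm edge to edge if the gap is (7.5 - 6.0) / 3 = 0.5 mm. With 1.5 mm contacts and 1.5 mm gaps, 7.5 mm holds (7.5 + 1.5) / 3 = 3 contacts. So 7.5 mm is a possible length for a four-contact lead with narrower gaps, but not for the lead in the background text.

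**Step 3: check whether the stated powers use the length.** The protocol gives no standard deviation, so I assume that the improvement percentages are read as proportions, with a two-sided 5% test on independent groups:

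z = [ |p1 - p2| x √n - 1.96 x √(2 x p̄ x (1 - p̄)) ] / √( p1(1 - p1) + p2(1 - p2) ), where p̄ is the mean of p1 and p2, n is the number per group, and power = Φ(z).

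- Efficacy Step 1, 0.85 v 0.25, n = 50 per group: z = (4.243 - 1.379) / 0.561 = 5.10. Power is above 99.9%, which matches the stated 100%.
- Efficacy Step 2, 0.85 v 0.60, n = 100 per target: z = (2.500 - 1.238) / 0.606 = 2.08. Power is 98.1%, which matches the stated 98%.

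Both figures are reproduced without any lead dimension.

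**Step 4: check whether the length determines 100.** The protocol gives no coverage formula, target density, map volume or minimum number of contacts per region. Replacing 7.5 mm with 10.5 mm therefore yields no new sample size. The density can only be illustrated. Assuming one lead per patient in all 100 (400 contacts spread evenly), it is 400 / 7.5 = 53.3 per mm against 400 / 10.5 = 38.1 per mm, a fall of 1 - 7.5 / 10.5 = 29%. The protocol does not state one lead per patient. The relative fall does not depend on the number of leads, but without a density target it cannot be judged adequate or inadequate.

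**Step 5: check whether the length enters the analysis.** *Target analysis* obtains contact positions from each patient's images. The field models in *Statistics* are simulations, and the section does not mention the 7.5 mm figure. It appears only in the sample-size parenthesis.

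**The case for a change.** The strongest case for acting is that the contradiction is visible within the protocol alone and concerns one of only three figures offered for the feature said to require the large sample. The overview also ranks the map above the comparison of targets. Correcting the figure would cost almost nothing, and no text outside the sample-size section supports 7.5 mm.

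The arithmetic part of this stands: the two figures cannot describe the same lead. The consequences do not.

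- The background passage is a general description of DBS and does not say that it specifies the trial's lead, so the slip may lie wholly in introductory text. Some figures are missing from the text at hand and might show the geometry.
- The stated aim of the large sample is cover of the periphery. That plausibly depends at least as much on the two deviation figures, which do not involve lead length.
- The choice of figure would not make the same 100 patients yield different maps. The implanted lead is what it is, and its contacts are located on imaging whatever length the planning paragraph cites.

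**Conclusion.** The mismatch is genuine, 10.5 mm against 7.5 mm (40%), but it is clerical. The documents do not show which figure is wrong, or that the background text was meant to describe the trial's lead. They give no rule by which either length would raise or lower the number of patients, and the 100% and 98% powers are reproduced without it. Contact positions are measured, so the comparison of Vim with cZi and the maps do not depend on the planning figure.

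This rests on two readings: that the improvement percentages behind the powers are proportions, and that the 7.5 mm figure is used only where it appears. An editor may wish to align the two sentences when the text is next opened. Doing so would alter neither what the trial does nor what it can conclude, so no change to the plan is called for.
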